Procedures. Eligible patients will be offered participation in this pilot study. The enrollment goal of 40 patients was chosen based on feasibility given the time-frame. Following informed consent, participants will be randomly assigned to one of the two study arms. All participants will be provided individual activity regimens, and be offered physical therapy, yoga, or tai-chi classes at the CMCVAMC. The activity goal will be participation in their activity regimen or classes at least twice per week, a frequency used in other studies promoting activity for chronic pain. Participants will self-report their activity, pain severity, functionality, and opioid use monthly via questionnaire and pill counts. Additionally, all participants will be provided an activity tracker to measure steps taken and instructed on use and data upload procedures. Upon the completion of their 12-week participation, participants are asked to complete an in-person exit survey answering questions about their experience in the study, the use of the FitBit activity watches, as well as the use of the FitBit application.

Those receiving the TEC-linked intervention will be familiarized with the text messaging process and the measures that will be administered via this technology. TEC will consist of a daily personalized text message from a dedicated research assistant reminding the patient to engage in their prescribed physical activity for the day. A second text message at the end of the day will direct the patient to return activity participation, pain severity, functionality, and opioid use data, and upload activity tracker data to the Way to Health (WTH) platform. The behavioral incentive provides the opportunity for subjects who meet their weekly activity goals to enter a lottery to receive either a small (\$30) or large (\$100) financial incentive. The lottery is structured such that subjects have an 18% chance/week of winning the small prize, and a 1% chance of winning the large prize. For those not meeting goals, they will be informed what they would have won had they met their goal. This design has been used in similar studies, with evidence showing the desire to avoid regret can be motivating.

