5.1.7. Will this study create a data repository for future studies? **NO**

5.1.7.1. If yes, describe and/or provide the following:

5.1.7.1.1. The type of data (identified or de-identified) including what protected health elements are to be collected.

5.1.7.1.2. The source from which data will be collected (e.g., subjects, non-research data repositories, research data repositories, publicly available, VA source, non-VA source).

5.1.7.1.3. How and where the data will be stored (e.g., electronic, paper records, approved VA-owned or VA-leased space).

5.1.7.1.4. How the data will be transmitted, if applicable.

5.1.7.1.5. How the data will be secured during storage, use, and transmission both during the conduct of the research protocol and after the protocol is completed.

5.1.7.1.6. **Plans to store data for future research.** If the data is stored for future research, there must be a description of a research data repository, its location, and its security measures.
[]

5.1.7.1.7. **Plans to share with others including other researchers (VA and non-VA).** If the data were collected through a research project, discussion of whether or not the original informed consent allowed for such reuse of the data and if the reuse is consistent with the HIPAA authorization that was obtained.
[]

5.1.7.1.8. **Justification for the use of any identifiers.**
[]

5.1.7.1.9. **Justification that the data requested represent the minimum necessary to conduct the research.**
[]

5.1.7.1.10. **A discussion of plans for obtaining informed consent and HIPAA Authorization, or for requesting the IRB to waive these requirements.** If the investigator requests that the requirement for a HIPAA Authorization be waived, justification for this request must be included in information submitted to the IRB.
[]

5.1.7.1.11. **In addition to the above, provide a Standard Operating Procedures Manual for the data repository. Contact IRB office for additional details.**

5.2. **Subject Recruitment Methods**

5.2.1. **State how many subjects will be needed:** 40 total subjects, with 20 in each arm of the study.

5.2.2. **Who will be responsible for recruiting potential subjects? Provide titles of individuals.**

The study team will include:

[name] – Principal Investigator
[name]- Co-Principal Investigator
[name]- Project Manager

5.2.3. **How will initial contact with potential subjects be made? (e.g., local clinics, physician referrals, letters to prospective subjects)**

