Veterans will be informed of the opportunity to participate in the study by [name] and provided with a copy of a study flyer, and study contact information. The study team will call the veteran 7 days provision of materials. If an individual is interested in the study, they will be asked to review the informed consent and be given the opportunity to ask questions. Once a signed informed consent is returned to the study team, a visit with the veteran will be scheduled to conducted eligibility and baseline surveys. The study team will provide the veteran a wearable device to track step counts and provide instructions to create an account by which they will transmit de-identified step data to the research team and how to access and use the WTH application.

5.2.4. **Will you be using any of the following methods to recruit subjects? (Check all that apply.)**

- Local database for which subjects have NOT given prior permission to be contacted for Research.
- Personal contact with patients over whom you have direct/indirect oversight
- Provider (Clinician) Referrals of potential subjects

5.2.5. Indicate the types of recruitment/advertisement materials that will be used: Check all that apply. Submit copies of recruitment materials, for IRB review.

X Not applicable; none to be used

- Fliers Newspapers Letters Websites Television
- Radio Audio Video Surveys
- Other (Specify, e.g. employee newsletters)

5.2.6. Non-Veteran Subjects will be given a copy of the Notice of Privacy Practices. ***NOT APPLICABLE***

5.3. **Compensation for Participation** - ***YES*** If yes, complete the following.

5.3.1. Summarize any financial compensation that will be offered to subjects.

All participants will receive \$75 to for completing the entire 12-week study. As noted above, they also have the possibility of receiving a financial incentive via a lottery process for meeting activity goals.

5.3.2. Provide the schedule for compensation.

5.3.2.1. Per study visit or session.

N/A

5.3.2.2. Total amount for entire participation.

\$75 if subject completes the entire 12-week study.

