6.2. **Provide a brief description of each individual's role in the study. Indicate who will have access to protected health information and who will be involved in recruiting subjects; obtaining informed consent; administering survey/interview procedures; and performing data analysis.**
The team includes: [name] (Principal Investigator), [name] (Co-Principal Investigator), [name] (Project Manager) and [name] (Statistician). These team members will only have access to PHI and will be working collectively to recruit subjects, obtain consents and administer surveys. [name] will perform data analysis.

6.3. **If applicable, provide information on any services that will be performed by contractors, including what is being contracted out and with whom.**
Not applicable.

6.4. **If applicable, provide information on any Memoranda of Understanding (MOUs) or Data Use Agreements (DUAs) that are being entered into, including with whom and for what reason.**
Not applicable.

Section 7: Genetic Testing

7.1. **Does the project involve genetic testing?** *Not Applicable, SKIP TO SECTION 8*

7.2. **Will specimens be kept for future, unspecified use?** *Choose an item.*

7.3. **Will samples be made anonymous to maintain confidentiality?** *Choose an item.* *(If there is a link, it is not anonymous. Coding is not anonymous.)*

7.4. **Will specimens be destroyed after the project-specific use is completed?** *Choose an item.*

7.5. **Will specimens be sold in the future?** *Choose an item.*

7.6. **Will subjects be paid for their specimens now or in the future?** *Choose an item.*

7.7. **Will subjects be informed of the results of the specimen testing?** *Choose an item.*

7.8. **Are there any implications for family members based on specimen testing results?** *Choose an item.*

7.8.1. **If answer to section 7.8 is yes, they may be subjects.**

7.9. **Will subjects be informed of results obtained from their DNA?** *Choose an item.*

7.10. **Explain if the study is looking for an association between a genetic marker and a specific disease or condition, but at this point it is not clear if the genetic marker has predictive value.**

7.11. **Describe if the study is based on the premise that a link between a genetic marker and a specific disease or condition is such that the marker is clinically useful in predicting the development of that specific disease or condition.**

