7.12. **Will the subject be notified of the results and the provision for genetic counseling?** *Choose an item.*

Section 8: International Research

8.1. **Does this study involve international research?** *NOT APPLICABLE* If no, go directly to section 9.

Section 9: Statistical Analysis

- 9.1. **Include statistical power calculations and the assumptions made in making these calculations.**
Being a pilot study, the enrollment goal of 40 patients was chosen based on feasibility given the time-frame as opposed to formal power analysis.
- 9.2. **Define plans for data and statistical analysis, including key elements of the statistical plan, stopping rules and endpoints.**
Data from the clinical trial will be analyzed using statistical software in SAS or R. Changes in pain severity, function, opioid analgesic use and physical activity over time will be compared between subjects assigned to each study arm. Regression analyses will be completed to assess if baseline patient characteristics impact the efficacy of the TEC-linked behavioral incentive intervention on key study outcomes.
- 9.3. **Provide sample size determination and analysis (include anticipated rate of screen failures, study discontinuations, lost to follow-up, etc.)**
See above.
- 9.4. **Describe how, where and by whom the data will be analyzed.**
The data will be analyzed by [name] and [name] with the help of a contracted statistician ([name]).

Section 10: References

1. Nahin RL. Estimates of pain prevalence and severity in adults: United States, 2012. *J Pain*. 2015;16(8):769–780.

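### The plan does not say that randomisation waits for the post-consent eligibility and baseline visit, and it describes no step period before the intervention starts

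*Combined protocol and SAP*

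**What the plan says.** All references are to the combined protocol and SAP.

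- **5.1.1, Procedures.** Eligibility comes before the offer: "Eligible patients will be offered participation in this pilot study". Then: "Following informed consent, participants will be randomly assigned to one of the two study arms". Nothing is named between consent and assignment.
- **5.2.3, initial contact.** "Once a signed informed consent is returned to the study team, a visit with the veteran will be scheduled to conducted eligibility and baseline surveys". Handing out the tracker and explaining the Way to Health platform belong to the same part of the process. Assignment is not mentioned.
- **5.2.1 and 9.1.** The target is "40 total subjects, with 20 in each arm of the study", a number "chosen based on feasibility given the time-frame as opposed to formal power analysis".
- **9.2.** "Changes in pain severity, function, opioid analgesic use and physical activity over time will be compared between subjects assigned to each study arm". No reference time point, analysis set, or rule for a patient found ineligible after assignment is given.
- **4.1.** The primary outcome has two parts: questionnaire-reported activity and tracker-measured mobility. (Section 3 lists daily steps among the secondary outcomes.)
- **Masking.** The double-blind box in 5.1.2 is not ticked. Section 5.6.1.6 codes the arms by letter until the analysis is finished, which concerns the analysis and not data collection. Under 6.2 one team is "working collectively to recruit subjects, obtain consents and administer surveys".

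**The concern.** In an unmasked trial with self-reported outcomes, eligibility and baseline need to be fixed before anyone knows the arm. Here assignment is tied only to consent, and the visit that settles eligibility and baseline also comes after consent. No section puts one before the other.

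If a site assigned patients as soon as consent came back, two things could happen. Participants could describe their baseline activity knowing whether they were in the lottery arm, and 9.2 compares changes from a starting level that this answer may supply. Patients could also be found ineligible after assignment. At least two criteria call for judgement: willingness to comply, and disability that rules out gains in activity.

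A related gap holds under any order. The tracker first reaches the patient around the visit in 5.2.3, and no interval is set aside to count steps before the texts and lottery begin. A comparison of changes in steps then has no stated pre-intervention reference.

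**Working it through.** **1. The order of steps.** Two sequences fit the text.

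| Sequence | Fits 5.1.1 on randomisation? | Fits 5.2.3? | Consequence |
|---|---|---|---|
| Consent, visit, randomisation | Yes: assignment is after consent | Yes: the visit is after consent | Eligibility and survey baseline precede assignment |
| Consent, randomisation, visit | Yes | Yes | Survey baseline may be given with the arm known; ineligibility may surface after assignment |

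Sections 5.1.2, 5.5, 5.6.1.6, 6.2 and 9.2 contain nothing that chooses between them. On eligibility the two sections do differ in wording: 5.1.1 has it known before the offer, 5.2.3 has it assessed after consent.

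**2. The plan's own figure.** 2 × 20 = 40 agrees with the stated total. As the number rests on feasibility, there is no alpha, SD or power to reproduce.

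**3. Illustration of a baseline shift.** All inputs except n = 20 per arm are assumed: unit SD at both times, two-sided 5% level, normal approximation, baseline to follow-up correlation r of 0.5 or 0.7, and a shift b in the reported baseline of one arm.

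- Change score: absolute bias = b; SE = sqrt(2(1 − r) × 2/20). At r = 0.5, SE = sqrt(0.100) = 0.316 SD; at r = 0.7, SE = sqrt(0.060) = 0.245 SD.
- Baseline-adjusted (ANCOVA): absolute bias = r × b; SE = sqrt((1 − r²) × 2/20).
- Type I error = 1 − Φ(1.96 − bias/SE) + Φ(−1.96 − bias/SE).

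| Shift b (SD) | Change score, r = 0.5 to 0.7 | ANCOVA, r = 0.5 to 0.7 |
|---|---|---|
| 0.1 | 6.2% to 6.9% | 5.4% to 6.1% |
| 0.2 | 9.7% to 12.9% | 6.5% to 9.5% |
| 0.3 | 15.8% to 23.2% | 8.5% to 15.3% |
| 0.5 | 35.3% to 53.2% | 15.0% to 34.1% |

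Example: b = 0.2, r = 0.5 gives 0.2/0.316 = 0.632, and the formula returns 9.7%. Baseline adjustment reduces the effect but does not remove it.

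**4. Illustration of late exclusions.** Section 9.3 gives no screen-failure rate. If 5% to 10% of 40 proved ineligible after assignment (assumed), that is 2 to 4 patients. The difference detectable with 80% power (assumed) is (1.960 + 0.842) × sqrt(2/n):

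- 20 per arm: 0.886 SD.
- 19 per arm (2 lost evenly): 0.909 SD; power at 0.886 SD is 78.0%.
- 18 per arm (4 lost evenly): 0.934 SD; power 75.7%.
- 20 against 16 (4 lost from one arm): 2.802 × sqrt(1/20 + 1/16) = 0.940 SD; power 75.2%.

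The loss of precision is small. Selection made with the arm known would be the larger worry, and it cannot be quantified from the documents.

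**The case against.** The strongest reply is that consent, then visit, then randomisation satisfies both sections literally and is the ordinary way to run a trial. Section 5.2.3 answers a question about recruitment, so its silence on assignment is natural. A pre-screen before the offer with confirmation after consent would explain the two statements on eligibility. This stands: the documents leave the order open and do not state a wrong one.

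A reader might infer more, and the documents do not support it:

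- **That patients are randomised before eligibility and baseline are settled.** No section says so.
- **That ineligible patients would be dropped unequally between arms, or replaced.** Section 5.5.2 foresees no withdrawal without the subject's consent, no replacement is described, and the criteria are the same for both arms. Unequal loss is a possibility only.
- **That baseline pain would be biased.** Section 5.10.1 lists background, technology and present activity level as the content of the baseline questionnaires. A pain baseline at this visit is not documented.
- **That every outcome in 9.2 is affected.** Section 9.2 defines no change score, measures are repeated during follow-up, and tracker steps are recorded by a device.

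Pilot status explains the absence of a power calculation. It does not settle the order of steps, and nothing masks participants or survey staff at baseline.

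**Conclusion.** The point holds as an unspecified order together with inconsistent wording on eligibility. Assignment before the eligibility and baseline visit is permitted but not required. Were it to happen, the exposed items would be the self-reported baseline activity and the composition of the arms.

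The size of any bias is unknown. The type I error range of 9.7% to 12.9% for a 0.2 SD shift, and the 2 to 4 late exclusions, rest wholly on assumed inputs and on the less favourable sequence; the documents supply neither a shift nor an ineligibility rate. No direction of bias is claimed.

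The lack of a described pre-intervention step period does not depend on which sequence is used. It matters because 4.1 counts tracker mobility in the primary outcome and 9.2 compares changes over time. Neither gap can be repaired once patients have been enrolled.

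**What to change.** 1. Reconcile 5.1.1 and 5.2.3 to one order: consent; eligibility confirmed; baseline surveys and first pill count completed and locked; then randomisation and disclosure of the arm. If a pre-screen before the offer is intended, say so and call the post-consent step a confirmation.
2. In 9.2, state that all randomised participants are analysed as assigned, including anyone later found ineligible.
3. Hand out the tracker at the same visit and record a short baseline step period before the first text or lottery. Name it in 9.2 as the reference or covariate for the step analysis. If it can also end before the arm is disclosed, it will be free of any reaction to assignment.

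Cost: items 1 and 2 are protocol wording and use the visit already planned. Item 3 delays each participant's start by a few days. N stays 40.

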Measures. The validated NIH PROMIS measures will be utilized to measure key study outcomes. Opioid use will be collected via the WTH Medication Adherence measure and monthly pill counts, and physical activity collected by self-report and a wearable activity tracker. In addition to collection of baseline demographic data and study experience data, study measures will be administered at the specified time points to evaluate the efficacy of the TEC intervention:

Measure	Tool	TEC administration
---------	------	--------------------

Pain severity	PROMIS Pain Intensity	Daily via text
Function	PROMIS Pain Interference	Daily via text
Opioid use	Medication Adherence tool, Pill counts	Daily Beginning and End
Physical activity	Stanford exercise questionnaire Wearable activity tracker	Weekly via text Weekly download
Anxiety, depression, general well-being	PROMIS-29 profile PHQ9	Monthly Monthly

Investigative team: Our interdisciplinary team includes a wealth of experience, including nationally known researchers in chronic pain ([name]), as well as the medical director of the new Pain-PACT ([name]). In addition, our team boasts expertise in connected health interventions using behavioral incentives ([name]).

Study Timeline. Study start-up procedures, including IRB approval and development of text messaging intervention, will take place during the first 3 months of the funding period. Subject recruitment will begin in month 4 and end in month 7, with data collection completed by study month 10. Months 11 and 12 will be devoted to data analysis and dissemination activities.

5.1.2. **What research methods will be used in the project? *Check all that apply.***

 Surveys/Questionnaires	 Interviews	 Audio Taping
 Behavioral Observations	 Chart Reviews	 Video Taping
 Focus Groups	 Randomization	 Double-Blind
 Control Group	 Placebo	 Withhold/Delay Treatment
 Specimen Collection	 Deception	 Telephone Survey

X Other (Describe) Mobility tracking via a wearable device.

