5.10. Information Security

5.10.1. **List the data/information that will be stored (including signed, original informed consent and HIPAA authorization forms, if applicable, case report forms, etc.)**

Stored data and information will include: patient information including name, last 4 of SSN, date of birth, BMI, medical, problem list, signed, original informed consent forms, medication usage, baseline questionnaires capturing participants' sociodemographic information, technology

assessment, and current level of physical activity, any responses from follow-up phone/in-person interviews/surveys.

5.10.2. **Describe the steps that will be taken to secure the data (e.g., training, authorization of access, password protection, encryption, physical controls, Certificates of Confidentiality and separation of identifiers and data).**

All study personnel will complete the required human subjects, HIPAA, and information security and privacy trainings at the VA. Each Veteran who enrolls in this study will be assigned a unique, random patient ID number generated for the purposes of this study. To protect each participant's identity, the link between the Veteran's name, last 4 of SSN, date of birth, and patient ID number will be a password protected file stored on a secure VA server and accessible only to research staff. In all subsequently created analytical files, participants will only be identified by their patient ID number, without inclusion of his/her name, SSN, or date of birth. Subject questionnaires will be either directly inputted into a computer database or written onto paper forms and then transferred to a database at a later time. Interview transcripts will be produced electronically and will be housed on a secure VA server as well. No results will be reported in a personally identifiable manner.

5.10.3. **Indicate how and where data/information will be stored, and specify pertinent security systems.**

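### The self-reported primary questionnaire has no schedule and mode fixed for both arms, so the plan permits unlike self-reports to be compared while only the TEC arm can win cash for activity

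*Combined protocol and SAP*

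**What the plan says.** Section 4.1 names two primary components: activity participation on the Stanford questionnaire, and mobility on a wearable tracker. It gives no time point or summary measure for either.

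Section 5.1.1 describes collection in three places.

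- Procedures, in the paragraph about all participants: "Participants will self-report their activity, pain severity, functionality, and opioid use monthly via questionnaire and pill counts". The activity instrument and its mode are not named.
- Procedures, in the paragraph about TEC recipients: an evening text asks for the day's activity, pain, function and opioid data, "and upload activity tracker data to the Way to Health (WTH) platform".
- The Measures table, whose only schedule column is headed TEC administration, gives "Weekly via text Weekly download" for the Stanford and the tracker respectively. There is no usual-care column.

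Section 5.10.1 lists baseline questionnaires that cover "current level of physical activity", again without naming an instrument.

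On the incentive, 5.1.1 sets the target, "The activity goal will be participation in their activity regimen or classes at least twice per week", and offers a chance for "subjects who meet their weekly activity goals to enter a lottery". Its design paragraph puts the lottery in the TEC arm.

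The whole statement of the comparison in 9.2 is: "Changes in pain severity, function, opioid analgesic use and physical activity over time will be compared between subjects assigned to each study arm".

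**The concern.** A between-arm difference on a self-reported outcome can be read as a difference in behaviour only if both arms are asked the same thing, equally often and in the same way. Here the plan can be followed to the letter with TEC participants answering the Stanford weekly by text and usual-care participants answering some monthly questionnaire in another form. Frequent prompting and a different mode can each shift answers without any change in activity.

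The lottery adds a second route. If a participant's own report decides whether the weekly goal was met, only TEC participants have a financial reason to report generously, about the same kind of behaviour that the Stanford measures.

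What is at stake is how to interpret one primary component. The tracker is worn in both arms and is a useful check, but a partial one: it counts steps, so it cannot fully confirm or refute a reported gain in yoga or tai chi.

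**Working it through.** There is no power calculation to reproduce. Section 9.1 chooses 40 patients on feasibility, and 5.2.1 splits them 20 and 20, which agrees. The check is therefore mainly a reading of the sections together.

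**1. Which Stanford assessments could be compared.** Over the 12-week intervention, a weekly schedule gives 12/1 = 12 assessments and a monthly one about 12/4 = 3. Three readings fit the text:

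| Reading | TEC | Usual care | Matched? |
|---|---|---|---|
| Monthly questionnaire is the Stanford in both arms, and 9.2 uses it | about 3 | about 3 | In number; mode not stated |
| Measures table is the schedule for everyone | 12, by text | 12, by text | Yes |
| Weekly text is TEC only, usual care reports monthly, and 9.2 uses everything | 12, by text | about 3, mode not stated | No |

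The column heading supports the third reading. So does the Procedures text, which introduces the text-administered measures to TEC recipients. The position of the monthly sentence, in the all-participants paragraph, supports the first. Section 5.10.2 allows direct computer entry or paper for questionnaires, so it does not settle the mode. Section 9.2 excludes none of the three.

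**2. What decides lottery entry.** The documents offer several candidates and choose none: evening text replies, uploaded tracker data, the weekly Stanford, attendance at the on-site classes (no attendance record is described), or the step-goal data that 5.10.3 says the platform collects. If device data or attendance decide entry, the motive to inflate reports largely disappears. If self-report decides it, the motive exists in TEC only, and it would still have to carry over into the Stanford answers to affect the primary comparison.

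**3. Context figures, which do not measure bias.**

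- Expected lottery value of a qualifying week: 0.18 x $30 + 0.01 x $100 = $5.40 + $1.00 = $6.40. The study payment is $75/12 = $6.25 per week. The incentive is thus about as large as the payment for taking part.
- Precision, assuming a two-sample comparison with equal SDs and all 20 per arm analysed: 95% CI half-width = t(0.975, 38) x sqrt(2/20) = 2.024 x 0.316 = 0.64 SD.

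Neither figure says how large a reporting difference would be. Nor would a larger sample help, because a reporting difference cannot be separated from a real effect on the same questionnaire at any sample size.

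**The case against.** The strongest reply is that a matched assessment probably already exists. The monthly self-report is described for participants in general, and the Stanford is the only self-report activity tool that the plan names, so it is the natural candidate. The Measures column may also be a general schedule: it includes items not marked as sent by text, such as the monthly "PROMIS-29 profile PHQ9", and the sentence that introduces the table does not limit it to one arm. Every participant must own a phone that can text, the recruitment text has participants shown how to use the platform's application, and the exit survey asks about phone surveys and daily reminders without separating the arms. In addition, this is a 40-patient pilot, the arms are coded until analysis is complete (5.6.1.6), and the tracker gives a primary component less exposed to reporting.

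Much of this stands. A reader might infer that the plan sets 12 weekly answers against 3 monthly ones, or that TEC participants are paid on their own word. The documents support neither as fact. The first needs the Stanford to go weekly to TEC only and the analyst to use all of those texts despite shared monthly data. The second needs self-report to decide lottery entry, which is nowhere stated.

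These points show that a harmless reading exists. They do not show that the plan specifies it. Coded arms do not change how participants were asked or why they answered as they did. Pilot status is not a full answer either, because Section 3 says that the results will be used to judge which strategies work.

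**Conclusion.** The concern holds as a gap in design and specification, not as a demonstrated bias. As written, the plan permits a primary component to be compared on self-reports that differ between arms in frequency and mode, while cash for meeting an activity goal goes to one arm. That last point takes the design paragraph of 5.1.1 over the looser wording of 5.3.1.

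The size of any effect on the result cannot be derived, and none is claimed. The figure of about 12 against 3 assessments is the most unequal of the readings set out, not a prediction.

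The gap should be fixed rather than merely noted. Unmatched collection cannot be repaired in the analysis, and matched collection is cheap at contacts already planned. Confidence is medium, because the investigators may already intend the monthly questionnaire to be the Stanford in both arms.

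**What to change.** In 5.1.1, name the Stanford as the activity instrument at baseline and at the monthly self-report, given to both arms at the same times and in the same mode. Keep these answers separate from lottery reporting, and tell participants that they do not affect lottery entry.

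In 9.2, base the between-arm Stanford comparison only on those common assessments and treat the weekly TEC texts as intervention data. Report tracker steps beside the result, without requiring them to agree before an activity effect is claimed.

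Cost: if the Stanford is not already used at baseline and monthly, up to (1 + 3) x 40 = 160 added administrations, with some burden on participants, and fewer TEC questionnaire points in the comparison. If it is already used there, the change is largely wording, plus one common mode.

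Four separate clarifications belong in the same revision:

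- State which data decide lottery entry. For a home regimen this may still have to be self-report.
- Reconcile 5.1.1 with 5.3.1 on who may enter the lottery.
- Reconcile the participation goal in 5.1.1 with the step goal in 5.10.3.
- Reconcile daily steps as a secondary outcome (Section 3) with tracker mobility as primary (4.1).
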